Proposed Research Protocol Form Northwestern University Feinberg School of Medicine

Department of Anesthesiology Research Committee

Title: The association between fluid administration, oxytocin administration, and fetal

heart rate changes.

Principal Investigator: [name]

Co-investigator (s): [name]; [name]; [name], Pharm D.

Affiliation: Department of Anesthesiology, Department of Obstetrics and Gynecology, Section

of Maternal Fetal Medicine; Northwestern University Feinberg School of Medicine

Institution: NMH

1.0 Research Aims:

.1 Research Questions(s): 1. Is there an association between the amount of intravenous

fluid administered prior to the initiation of combined spinal-epidural (CSE) analgesia

and post-analgesia fetal heart rate (FHR) non-reassuring fetal heart rate patterns? 2. Is

there an association between the rate of oxytocin administration and non-reassuring

FHR changes after the initiation of combined spinal-epidural (CSE) analgesia?

.2 Hypotheses: Patients who receive a 1000 mL fluid bolus and lower rates of

oxytocin administration will have fewer non-reassuring FHR changes.

2.0 Research significance:

Background:

Combined spinal-epidural (CSE) analgesia is a well-accepted technique for labor

analgesia. The incidence of fetal heart rate changes after the initiation of neuraxial

analgesia has been reported between 3-23% (1,2) and it is controversial whether the risk

is increased with a CSE technique compared to an epidural analgesia technique. This

06/07/07

1 of 11

wide range in reported risk may be due to fluid and oxytocin management prior to and during the initiation of neuraxial analgesia.

There are many factors that contribute to alterations in the fetal heart rate including stage of labor, fetal head compression, cord compression, and uteroplacental insufficiency. Oxytocin is used in labor and delivery to increase the frequency of contractions and augment uterine contractile strength, thereby establishing a regular pattern of labor. However, the administration of exogenous oxytocin in the presence of an uncoordinated labor pattern confers a risk for increase in uterine contraction frequency, resulting in inadequate relaxation periods. This leads to an increase in the basal tone of the uterus, which may lead to a tetanic contraction with risk decreased uteroplacental blood flow and fetal hypoxemia (3). Since the introduction of oxytocin for labor induction in 1948, there have been multiple protocols for the administration of oxytocin, both for labor induction, as well as for augmentation of labor. Many institutions use an active management of labor protocol (AMOL) to facilitate labor and delivery through oxytocin management. Use of the AMOL protocol decreases the duration of labor and the Cesarean delivery rate for dystocia (4). The evidence is divided as to the effect of highversus low-dose oxytocin administration on fetal heart rate abnormalities (5-9). Merrill et al. randomized patients to low-versus high-dose oxytocin for augmentation or induction of labor (8). Oxytocin was decreased or discontinued more commonly in the high-dose group, both for uterine hyperstimulation and FHR abnormalities. In contrast, a study comparing high-dose oxytocin management with standard care found that there were no differences in fetal outcomes or the incidence of fetal distress between groups (9). One of the limitations of the previous studies is that the labor analgesia was not standardized;

and consisted of either traditional epidural (high dose) analgesia or intravenous opioids.

Labor analgesia itself has been implicated as a cause of non-reassuring fetal heart rate tracings. The combination of low-dose combined spinal epidural analgesia and the high-low-dose oxytocin have not been evaluated.

One of the proposed mechanisms for non-reassuring fetal heart tracings after initiation of analgesia is that the pain relief from neuraxial analgesia causes a decrease in catecholamine release by the sympathetic nervous system (4). The subsequent decrease in the circulating epinephrine concentration contributes to an increase in uterine tone, as epinephrine is a potent tocolytic agent. The increased tone, in turn, leads to a decrease in placental blood flow, and eventually fetal bradycardia. Prior to initiation of neuraxial analgesia, an intravenous fluid bolus is usually given in order to prevent hypotension due to the sympathectomy associated with the neuraxial administration of local anesthetic. The fluid bolus mitigates hypotension due to relative hypovolemia. However, it may also dilute oxytocin (both from endogenous and exogenous sources), or decrease endogenous release of oxytocin, thus decreasing the risk of uterine hyperstimulation. Preliminary evidence suggests that peri-analgesia fluid management influences uterine activity and fetal heart rate patterns (10,11) In an underpowered study, Kinsella suggested that a fluid bolus may be associated with a decreased incidence of non-reassuring fetal heart rate patterns (10). Cheek and colleagues demonstrated a decrease in uterine activity associated with a 1 L, compared to 0.5 L or no fluid bolus before initiation of epidural analgesia (11). A Cochrane database review of the literature found that intravenous preloading may help to reduce maternal hypotension, but using lower doses of local anesthetic and opioid-only blockade also reduces the incidence of hypotension and may reduce or

06/07/07 V 1.1 eliminate the need for preloading to prevent maternal hypotension (1). There were no differences between preloading and no-preloading with regards to fetal heart rate abnormalities, however, the wide confidence intervals could not refute or confirm a difference (1). Therefore, the administration of a fluid bolus prior to the initiation of neuraxial analgesia remains controversial and many institutions do not routinely administer a bolus.

The optimal fluid and oxytocin management in the peri-analgesia initiation period in terms of affects on uterine activity, uteroplacental perfusion, and fetal oxygenation, is not known. Anecdotally, some institutions routinely administer a fluid bolus before initiation of low-dose bupivacaine/opioid neuraxial analgesia, whereas others do not. Some institutions arbitrarily decrease (or do not increase) the oxytocin infusion rate during initiation of analgesia. We hypothesize that the combination of fluid administration and lower doses of oxytocin administration will cause fewer adverse fetal heart rate changes in the first 60 minutes following initiation of labor analgesia.

- .2 Significance: Fetal heart rate patterns are an important parameter in the diagnosis of non-reassuring fetal status. Combined-spinal epidural analgesia is a method of initiating labor analgesia used by approximately 90% of the parturients at Prentice Women's Hospital. Optimizing the variables which could affect fetal heart rate patterns at the time of initiation of analgesia, such as fluid administration and oxytocin management, could help us provide better care for our patients and their fetuses.

### 3.0 Investigational Plan

.1 Study design: Double blinded randomized, controlled study.

#### .2 Methods:

- fetal heart rate tracings after the placement of CSE. Group sample sizes of 88 in each of the four groups achieves 80% power to detect a difference among the groups assuming an effect size (W) of 0.1900 using a 3 degrees of freedom Chi-Square Test with a significance level (alpha) of 0.05. The incidence of fetal heart rate changes was estimated based on data from Kinsella, et al (10). The proportion of subjects with adverse fetal heart rate changes in the low-oxytocin and fluid bolus treatment group is estimated to be 8%, and the proportion in the low-oxytocin, no-fluid bolus control group is estimated to be 23%. The proportion in the high-oxytocin groups is assumed to be 15% and 25% with and without a fluid bolus respectively. Therefore 380 patients will be enrolled to account for patient drop-out or ineligibility.
- .2.2 Subject entry, exclusion and dropout criteria: Healthy nulliparous or multiparous women with a term (>36 week gestation), singleton pregnancy in spontaneous labor or with spontaneous rupture of membranes, who request neuraxial analgesia, and will be managed by the active management of labor protocol (AMOL) and receive oxytocin, or receive oxytocin augmentation per PWH's protocols, will be eligible to participate in the study. Maternal exclusion criteria will include the presence of any systemic disease (e.g., diabetes mellitus, hypertension, preeclampsia); use of chronic analgesic medications; prior administration of systemic opioid labor analgesia; non-vertex presentation; scheduled induction of labor; or any contraindication to neuraxial analgesia.

2.3 Protocol specific methods: Eligible women will be asked to participate shortly after admission to the Labor & Delivery Unit at Prentice Women's Hospital during the routine pre-anesthetic interview. Informed, written consent will be obtained. Block randomization based on parity, via a computer generated random number table, will be performed and group assignments will be concealed in sealed, opaque envelopes. At the time of request for labor analgesia, group assignment will be determined by opening an opaque envelope. Patients will be randomized to one of four groups:

Group Assignment	Fluid Administration	Oxytocin Regimen
A	1000 mL bolus	Routine oxytocin
В	1000 mL bolus	Half-dose oxytocin
С	No bolus	Routine oxytocin
D	No bolus	Half-dose oxytocin

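### The stated effect size W = 0.1900 does not follow from the plan's four proportions (which give W = 0.177), and with 88 per group it gives 86% power, not 80%

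*Combined protocol and SAP*

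**What the plan says.** Section 3.0, .2 Methods, gives every input of the power calculation in one paragraph.

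- Size, power and effect: 88 women in each of four groups "achieves 80% power to detect a difference among the groups assuming an effect size (W) of 0.1900".
- Test: "using a 3 degrees of freedom Chi-Square Test with a significance level (alpha) of 0.05".
- Low-oxytocin rates: the "low-oxytocin and fluid bolus treatment group is estimated to be 8"%, and the "low-oxytocin, no-fluid bolus control group is estimated to be 23"%.
- High-oxytocin rates: "The proportion in the high-oxytocin groups is assumed to be 15% and 25% with and without a fluid bolus respectively".
- Enrolment: 380 women, to cover drop-out and ineligibility. No drop-out rate is stated.

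Section 4.0, .2 Data evaluation, plans a chi-square comparison of the primary endpoint across the four groups, which is the test used for the sample size.

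**The concern.** For a chi-square test on a 2 × 4 table with equal groups, W is fixed by the four proportions. Power is then fixed by W, the total number, the degrees of freedom and alpha. The paragraph states all of these, so it is over-determined and can be checked without any outside source.

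W is the quantity on which the power claim is conditioned. If it is wrong, the sentence cannot be reproduced, and a reader cannot tell from it whether the group size, the effect size or the rates are at fault. It also matters for judging losses. Someone working from the printed W would conclude that about 304 evaluable women are enough, which may not be so under the rates the plan expects.

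**Working it through.** **Inputs** (all from the sample-size paragraph): n = 88 per group, N = 4 × 88 = 352; W = 0.1900; 3 df; alpha = 0.05; power 80%; rates 0.08, 0.23, 0.15, 0.25; equal allocation.

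**Method.** Power = P(χ′²(3 df, λ) > 7.815), where λ = N × W² and 7.815 is the 95th percentile of chi-square on 3 df. Power of 80% requires λ = 10.90.

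**Step 1: the plan's figure from its stated W.**
- W² = 0.1900² = 0.0361
- λ = 352 × 0.0361 = 12.71
- Power = 86.2%, against 80% stated
- N for 80% power: 10.90 / 0.0361 = 302.0, so 303 women, or 76 per group

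The stated 80% is not reproduced.

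**Step 2: W from the four rates.**
- Mean rate = (0.08 + 0.23 + 0.15 + 0.25) / 4 = 0.1775
- Squared deviations: 0.009506, 0.002756, 0.000756, 0.005256; mean = 0.004569
- Mean rate × (1 − mean rate) = 0.1775 × 0.8225 = 0.14599
- W² = 0.004569 / 0.14599 = 0.03129, so W = 0.1769

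**Step 3: power at that W.**
- λ = 352 × 0.03129 = 11.02
- Power = 80.4%
- N for 80% power: 10.90 / 0.03129 = 348.4, so 349 women, or 88 per group after rounding up

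This reproduces both the 88 and the 80%. The W that gives exactly 80% at N = 352 is 0.176.

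| | W = 0.1900 (stated) | W = 0.1769 (from the rates) |
|---|---|---|
| Power at 352 | 86.2% | 80.4% |
| N for 80% power | 303 | 349 |
| Per group | 76 | 88 |

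**Step 4: size of the discrepancy.** 0.1900 / 0.1769 = 1.07, and 0.0361 / 0.03129 = 1.15. The stated W is 7% too large, and the noncentrality 15% too large.

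**Step 5: other ways to reach 0.1900 or 80%.**
- Rounding: moving each rate by up to 0.5 percentage points gives W between 0.165 and 0.189, still short of 0.1900.
- Other definitions of the effect size: unpooled variance gives 0.180, the standard deviation of arcsine-transformed rates 0.188, and a divisor of k − 1 gives 0.204. None equals 0.1900.
- Other test settings at W = 0.19 and N = 352: 4 df gives 82.7%, 5 df gives 79.6%, and 3 df with alpha 0.025 gives 79.2%. All contradict the stated 3 df and 0.05.
- Enrolled rather than evaluable women: N = 380 with W = 0.19 gives 88.9%, further from 80%.

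**Step 6: losses judged against the printed W.** At W = 0.19, 76 per group (304 women) appears to give 80%. Under the plan's rates, λ = 304 × 0.03129 = 9.51 and power is 73.8%. Simulating the Pearson test directly at 76 per group gives 76.7%. Both are below 80%.

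**The case against.** The strongest reply is that nothing operational depends on W. The rates, degrees of freedom, alpha, group size and power agree with one another, and the primary analysis does not use W. The error did not reduce the sample size: power at the stated W is higher than claimed, not lower. That all stands, and it limits the point to a correction of the text.

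The second reply is that the 304-women scenario is hypothetical. The plan has no step that judges losses against W. Reaching 304 from 380 would mean losing 76 women (20%), whereas the plan's margin is 28 (380 − 352, or 7.4%). This also stands: the scenario shows how the wrong figure could mislead, and does not describe something the plan does.

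Third, the noncentral chi-square is an approximation. Simulating the Pearson test at the plan's rates gives about 83.5% power at 88 per group, and about 82 per group already reaches 80%. The shortfall at 304 is then about 3 points rather than 6. This is a fair qualification of the trial's actual power. It does not rescue W = 0.1900, because the approximation is the standard calculation for a power statement in terms of W, and it reproduces the plan's 88 and 80% from the plan's own rates.

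Last, the opening of the paragraph is cut off in the text available for review, and the documents do not show where 0.1900 came from. Every input to the calculation survives, however, and nothing elsewhere in the documents reconciles the figure.

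**Conclusion.** The power statement is wrong as written. The four rates imply W = 0.177, not 0.1900, and at W = 0.1900 the planned 352 women give 86.2% power, not 80%. Because the rates, group size, power, degrees of freedom and alpha all agree, W is the figure to correct.

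The consequence is limited. On its stated rates the trial has at least its nominal 80% power (80.4% by the approximation, about 83.5% by simulation). The correction still deserves making, because W is the design figure on which the power claim rests. The conclusion assumes equal groups and the standard definition of W for a 2 × 4 table, both of which fit the paragraph.

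**What to change.** In the sample-size paragraph, replace the effect size of 0.1900 with 0.177, the value the four stated rates produce, and keep 88 per group and 80% power. If 0.1900 came from a different set of rates, the sponsor should state those rates and reconcile the paragraph with them.

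The cost is one number. With W corrected to 0.177, neither enrolment nor the analysis changes.

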# Oxytocin Management:

The Prentice Women's Hospital AMOL and oxytocin protocols will be used. At the time of request for analgesia, if the patient is in group A or C, the oxytocin management will continue as per the normal oxytocin or AMOL protocol.

If the patient is randomized to groups B or D, the dose of oxytocin currently being administered will be halved and not increased for the duration of the study period (60 minutes after the initiation of CSE). Care providers other than the Labor & Delivery nurse managing the fluid and oxytocin infusions, will be blinded to group assignment.

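### The envelope can be opened for a woman with no oxytocin running, but the half-dose rule needs a current dose to halve

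*Combined protocol and SAP*

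**What the plan says.** Three parts of section 3.0 of the combined protocol and SAP bear on this.

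- **Entry (.2.2 Subject entry, exclusion and dropout criteria).** Women must be in spontaneous labor or have spontaneously ruptured membranes, and scheduled induction is excluded. On oxytocin, the criterion is that they "will be managed by the active management of labor protocol (AMOL) and receive oxytocin", or receive augmentation under the hospital's protocols. The augmentation branch gives no timing.
- **Assignment (2.3 Protocol specific methods).** Women are approached soon after admission. Later, "At the time of request for labor analgesia, group assignment will be determined by opening an opaque envelope". The request is the only stated trigger.
- **Intervention (Oxytocin Management).** Also at the request, Groups A and C carry on under the unit protocol. In Groups B and D, "the dose of oxytocin currently being administered will be halved and not increased for the duration of the study period", which is 60 minutes after the start of the CSE.

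The data collection form (4.0, .1) records the oxytocin dose at CSE placement and the maximum dose in the next 60 minutes. It lists neither the dose at the request nor the time oxytocin was started.

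**The concern.** The entry criteria decide who is randomised, and Oxytocin Management decides what happens next. The second assumes a condition that the first does not impose. A woman can meet every entry criterion, request analgesia before oxytocin has been started, and be assigned to B or D with nothing to halve.

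Research question 2 asks about the rate of oxytocin administration. A woman without an infusion cannot contribute the intended comparison to it. If staff treat her alike under both regimens, she contributes no contrast. If the bar on increases is applied literally, B and D are held at zero while A and C may start oxytocin, which is a different contrast from half versus routine dose.

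This is hard to repair in the analysis. The dose at CSE placement is recorded after assignment. Between request and placement, oxytocin may be started in A and C but, read literally, not in B and D. Dropping women with a recorded dose of zero could therefore remove different kinds of women from different arms.

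**Working it through.** **Inputs from the sample size paragraph (3.0, .2 Methods).** The planned rates of adverse fetal heart rate changes are A (bolus, routine) 15%, B (bolus, half-dose) 8%, C (no bolus, routine) 25% and D (no bolus, half-dose) 23%. There are 88 women per group, so N = 352. The test is specified as "using a 3 degrees of freedom Chi-Square Test with a significance level (alpha) of 0.05".

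**Assumption.** The share f of randomised women without an infusion at the request is not in the documents. Values from 0 to 50% are shown, taken as equal in all four groups.

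**Step 1: reproduce the plan's power.** The mean rate is (15 + 8 + 25 + 23)/4 = 17.75%.

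W = √[mean of (pᵢ − p̄)² / (p̄(1 − p̄))] = √(0.004569/0.14599) = 0.177

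The noncentrality is 352 × 0.177² ≈ 11.0, which on 3 df gives 80.4% power. The required N is 349, or 88 per group. The stated 88 and 80% therefore follow from the four rates. The printed W of 0.1900 does not: it would give 86.2% power at N = 352. That is a separate matter, and the steps below use the rates.

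**Step 2: the oxytocin contrast.** The routine arms average (15 + 25)/2 = 20.0% and the half-dose arms (8 + 23)/2 = 15.5%, a difference of 4.5 points with 2 × 88 = 176 women per side. Two-sided power at 5% is Φ[(d − 1.96·SE₀)/SE₁], with SE₀ pooled and SE₁ unpooled:

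- SE₀ = √(2 × 0.1775 × 0.8225/176) = 0.0407
- SE₁ = √((0.20 × 0.80 + 0.155 × 0.845)/176) = 0.0407
- Power = Φ[(0.045 − 0.0798)/0.0407] = 19.6%

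If women without an infusion receive no contrast, d = 4.5 × (1 − f), here centred on 17.75%:

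| f (assumed) | Difference (points) | Power |
|---|---|---|
| 0 | 4.50 | 19.6% |
| 10% | 4.05 | 16.7% |
| 20% | 3.60 | 14.1% |
| 30% | 3.15 | 11.7% |
| 50% | 2.25 | 8.0% |

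**Step 3: the four-group test.** The result depends on the event rate among women without an infusion, which is also not given. Within each fluid stratum they could have the routine-arm rate, the half-dose-arm rate, or the midpoint. At f = 20%:

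- Routine-arm rate: B becomes 0.8 × 8 + 0.2 × 15 = 9.4% and D becomes 0.8 × 23 + 0.2 × 25 = 23.4%, so W = 0.164.
- Half-dose-arm rate: A becomes 0.8 × 15 + 0.2 × 8 = 13.6% and C becomes 0.8 × 25 + 0.2 × 23 = 24.6%, so W = 0.180.

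| f (assumed) | Routine-arm rate | Midway | Half-dose-arm rate |
|---|---|---|---|
| 10% | 77.2% | 79.2% | 81.2% |
| 20% | 73.8% | 78.1% | 82.1% |
| 30% | 70.3% | 77.0% | 83.1% |
| 50% | 63.3% | 75.3% | 85.4% |

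Power rises in the last column because the planned fluid effect is larger at half dose (23 − 8 = 15 points) than at routine dose (25 − 15 = 10 points). A simulation of 40,000 trials per setting put all levels somewhat higher but showed the same pattern: 83.3% at f = 0, then 75.8% (routine-arm rate) or 84.6% (half-dose-arm rate) at f = 20%.

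**Step 4: the enrolment allowance.** The plan enrolls 380 to cover drop-out or ineligibility, a margin of 28 women (28/380 = 7.4%). If 380 counts women consented and those without an infusion are not randomised, f = 20% leaves 380 × 0.8 = 304, below 352 before any other loss.

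**The case against.** The best defence is that the plan clearly has women on oxytocin in mind. Entry is limited to women who are to receive it. Oxytocin Management speaks of continuing or halving a current dose at the moment the envelope is opened. The margin from 352 to 380 allows for women who prove ineligible, and a woman without an infusion could be one of them. On this reading only a clarifying sentence is missing, and f may be zero.

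The point about intent stands, and so does the point that no loss has been shown. But the expectation was never made a criterion. Oxytocin Management excludes nobody, and nothing says that a woman without an infusion is ineligible.

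A reader might infer that the gap erodes the 80% power. The documents do not support that, for three reasons. They do not give f. The direction depends on an event rate they do not give either, and under the plan's own hypothesis women on no oxytocin might resemble the half-dose arms, in which case power rises. And the 80% belongs to a test of any difference among four groups ("Group sample sizes of 88 in each of the four groups achieves 80% power to detect a difference among the groups"). It was never power for the oxytocin contrast. The planned fluid contrast (11.5% v 24.0%, 87.0% power at 176 per side) supplies most of it.

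It is also fair to say that the oxytocin contrast is weak before any dilution, and that moving from about 20% to about 14% power does not create that weakness. The case for the change is that the assignment is undefined for these women.

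**Conclusion.** The entry criteria and the oxytocin rule do not fit together and must be reconciled. As written, the plan can randomise women who cannot receive the half-dose versus routine contrast of question 2.

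The inconsistency is certain from the text, but how often it would arise is unknown. If such women are managed alike under both regimens, the oxytocin difference shrinks in proportion to 1 − f; the fall to 3.6 points and about 14% power rests on the assumed f of 20% and the plan's own rates. If B and D are instead held at zero while A and C start oxytocin, a contrast remains, but it is not the planned one, and these figures do not describe it.

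No loss of the 80% four-group power should be claimed. This is a cheap improvement, not a demonstrated failure of the design.

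**What to change.** Add to 2.3 Protocol specific methods: *The envelope is opened only if an oxytocin infusion is running at the time of the request for labor analgesia. Consented women without a running infusion at that time are not randomised.*

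State in the sample size paragraph whether the 380 counts women consented or women randomised. The dose rules stay as they are.

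The cost is a short amendment and one check by whoever opens the envelope. Some consented women will not be randomised. If f is zero, nothing else changes. At an assumed f of 20%, randomising 380 would take 380/0.8 = 475 consented women who go on to request analgesia. The results would apply to women already on oxytocin at the request, which is the population the oxytocin rule already presumes.

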# Fetal heart rate tracing assessment:

Fetal heart rate tracings will be examined for 30 minutes before and 60 minutes after the initiation of analgesia by a perinatologist blinded to study group off-line after delivery. NICHD guidelines (12) will be used to assess FHR patterns. Non-reassuring FHR patterns will be defined as any one or more of the following: minimal or absent variability, late decelerations, and persistent deceleration (see Appendix).

.2.4 Risks/Benefits: All of the techniques and medications used in this study are routinely used for CSE analgesia during labor and for management of labor. The risks of the CSE procedure itself are unchanged by participating in this study. These risks include: epidural analgesia may not be effective, the epidural procedure may need to be repeated, pruritus, nausea, vomiting, or hypotension. Less common risks include maternal postdural puncture headache. Rare complications include maternal or fetal respiratory depression, total spinal anesthesia, a toxic reaction to the anesthetic agents, and bleeding or infection in

the epidural or spinal space that may lead to nerve damage. The risk of oxytocin administration includes nausea, vomiting, confusion, allergic reaction, uterine hyperstimulation, fetal bradycardia, or maternal cardiac arrhythmias. There are

no direct benefits to the patient for participating in the study.

4.0 Data Analysis:

.1 Data collection form: The following data will be collected:

Demographic data: age, race, height, weight, gravidity, parity, and gestational age.

history of prior inductions.

Labor data: time of rupture of membranes, cervical examination prior to placement of CSE (dilation, effacement, and station); start and stop time of fluid bolus, time of intrathecal injection, oxytocin dose at time of placement of CSE, vasopressor use and dose, maximum oxytocin dose in 60 minutes following placement of CSE, number of times oxytocin infusion is stopped or decreased for hyperstimulation or nonreassuring fetal status, time to complete cervical dilation, time of delivery, maximal

maternal body temperature in study period.

Mode of delivery: normal spontaneous vaginal, instrumental vaginal, Cesarean.

Neonatal data: 1- and 5-minute Appar scores; fetal umbilical cord gases (if taken);

birth weight; neonatal sepsis workup or ICU admission.

Fetal heart rate tracing data: see appendix

.2 Data evaluation:

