The primary endpoint is the incidence of non-reassuring fetal heart rate tracings during the first 60 minutes after the placement of CSE. Cross tabulation tables will be

constructed with the presence or absence of the endpoint as rows and the groups as

06/07/07 V 1.1

10 of 11

columns. Differences in the frequency among groups will be assessed using a X statistic. Exact tests will be computed using Monte-Carlo sampling of 10,000 samples

with a confidence level of 99%.

Secondary outcomes and demographics: Age, height, weight, gestational age, fetal

station, and frequency of contractions will be compared using ANOVA or Kruskal

Wallis ANOVA with post-hoc comparisons correction for multiple comparisons.

Binominal and ordinal data will be compared between groups using the X statistic or

the Fisher's exact test. A P < 0.05 will be required to reject the null hypothesis.

5.0 Interpretation of Anticipated Results:

We anticipate that the combination of fluid administration and lower doses of oxytocin

will cause fewer adverse fetal heart rate changes in the first 60 minutes following

initiation of labor analgesia.

6.0 Budget:

.1 Materials: No additional materials will be required as all of the materials used in

the study are routinely used in the management of patients.

.2 Labor Requirements: Existing anesthesia personnel on Labor & Delivery Unit.

.3 Presentation Cost: Anticipated presentations at MARC, SOAP and ASA meetings.

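### Randomisation is blocked on parity but the primary test ignores parity; if parity is prognostic, the test is mildly conservative and gives up a little power

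*Combined protocol and SAP*

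**What the plan says.** - **Randomisation (section 3.0 .2.3):** "Block randomization based on parity, via a computer generated random number table, will be performed". Section 3.0 .2.2 admits both nulliparous and multiparous women, so parity will vary. The parity categories and the block size are not stated.
- **Data collected (section 4.0 .1):** "Demographic data: age, race, height, weight, gravidity, parity, and gestational age". Parity is therefore available to the analyst.
- **Primary analysis (section 4.0 .2):** tables are to be "constructed with the presence or absence of the endpoint as rows and the groups as" columns, and the frequencies compared by chi-square. In addition, "Exact tests will be computed using Monte-Carlo sampling of 10,000 samples". Neither test has a parity layer, and how the exact test permutes is not stated.
- **Sample size (section 3.0 .2):** the calculation was done "using a 3 degrees of freedom Chi-Square Test with a significance level (alpha) of 0.05", which is the same unstratified test.

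No stratified test, parity-adjusted model or analysis by parity appears anywhere in the document.

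**The concern.** Blocking within parity forces the four groups to have nearly the same parity mix, so chance imbalance in parity no longer contributes to differences between groups. An unstratified chi-square does not know this. Its variance is the pooled binomial variance, which still includes the between-parity component. If parity is related to the outcome, that variance is too large for the design actually used, and the test rejects less often than its nominal 5%. An exact test that permutes across all women, as is usual for an unstratified table, has the same small conservatism; it is not a second problem.

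What is at stake is some power that the trial's own randomisation makes available. Bias and excess false positives are not at issue.

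**Working it through.** **1. The plan's own figure.** The planned rates for groups A, B, C and D are 15%, 8%, 25% and 23% (section 3.0 .2).

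- Mean rate = (15 + 8 + 25 + 23)/4 = 17.75%.
- Mean squared deviation = (2.75² + 9.75² + 7.25² + 5.25²)/4 = 45.69 squared points = 0.004569.
- W² = 0.004569/(0.1775 × 0.8225) = 0.03129, so W = 0.1769.
- Noncentrality at N = 4 × 88 = 352 is 352 × 0.03129 = 11.0. With 3 df and critical value 7.815, power is 80.4%.

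This reproduces the statement "Group sample sizes of 88 in each of the four groups achieves 80% power to detect a difference among the groups". The printed value, "assuming an effect size (W) of 0.1900", would instead give 352 × 0.0361 = 12.7 and 86.2% power. So 88 per group follows from the rates, not from the printed W. That mismatch is a separate matter and does not affect what follows.

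**2. Direction and approximate size.** Let f be the share of women in the higher-risk parity stratum, r1 and r0 the event rates in the two strata, and p the overall rate. The share of outcome variance explained by parity is

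R² = f(1 − f)(r1 − r0)²/[p(1 − p)].

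With balance within parity, the true level of the unstratified test is approximately P(χ²₃ > 7.815/(1 − R²)). For an assumed parity odds ratio (OR) of 3, f = 0.5 and p = 17.75%, the stratum rates are 25.3% and 10.2%, R² = 0.0394, the threshold becomes 7.815/0.9606 = 8.14, and the level is 4.3%.

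**3. Simulation.** Assumptions not in the documents: two parity strata; a common parity OR of 1 to 6; 30%, 50% or 70% of women in the higher-risk stratum; exact balance within parity. Marginal rates are held at 17.75% in every group (null) or 15/8/25/23% (planned). There are 200,000 trials per cell with 88 per group. The Pearson 3-df chi-square is compared with the 3-df Cochran-Mantel-Haenszel (CMH) general-association test stratified by parity.

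| Parity OR | Type I error of planned test, % (30/50/70% mix) | Power gain from stratifying, points (30/50/70% mix) |
|---|---|---|
| 1 | 5.0 / 4.9 / 5.0 | −0.1 / −0.1 / −0.1 |
| 1.5 | 4.9 / 4.8 / 4.9 | 0.1 / 0.1 / 0.0 |
| 2 | 4.7 / 4.7 / 4.7 | 0.5 / 0.5 / 0.3 |
| 3 | 4.2 / 4.3 / 4.6 | 1.5 / 1.3 / 0.8 |
| 4 | 3.8 / 4.0 / 4.3 | 2.6 / 2.1 / 1.2 |
| 6 | 3.1 / 3.6 / 4.1 | 4.2 / 3.2 / 1.7 |

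The stratified test holds 4.8-5.0% throughout. The planned test keeps 83.3-83.8% power in every cell, a little above the 80.4% from the noncentral approximation. Simulation error is about 0.05 points for type I error and 0.08 for power.

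**4. Is the blocking the cause?** A separate simulation used parity blocks of 8 instead of exact balance (100,000 trials per cell, 50% or 70% mix). At a 50% mix the planned test had a level of 4.5% at OR 2 and 4.2% at OR 3, and stratifying gained 0.5 and 1.4 points. When randomisation was not stratified by parity, the planned test stayed at about 5% (4.9-5.0%) at every OR tried, from 1 to 5. The conservatism therefore comes from blocking on the factor and then leaving it out.

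**5. Exact test.** In a smaller simulation (50% mix, 20,000 trials per cell, 999 permutations each), type I error at OR 1/2/3/6 was 4.7/4.5/4.1/3.3% when permuting across parity and 4.7/4.9/4.7/4.7% when permuting within it. The power gain was −0.1/0.4/1.7/3.3 points. Simulation error here is about 0.15 and 0.27 points. These figures, unlike those in step 3, were not checked by a second simulation.

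**The case against.** The strongest reply is that nothing is broken. The chi-square is the test the trial was powered for, it controls type I error, and it has more than the planned power. That stands, and it limits the point to an efficiency improvement.

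The benefit also depends on a parity effect that the documents never give. The background (section 2.0) does not list parity among the contributors to fetal heart rate change, and blocking may have been meant only for baseline comparability. Below a parity OR of 2 the gain is at most about 0.1 point. Gains above 2 points need an OR of 4 or more, whereas the largest planned treatment contrast, 25% against 8%, is an OR of (0.25/0.75)/(0.08/0.92) = 3.8. This also stands: the OR 4 and 6 rows show the range and are not an expectation. Exact balance is the most favourable case for stratifying. However, allowing for 380 randomised and 7.4% dropout (1 − 352/380), with blocks of 8, still gave 0.3-0.5 points at OR 2.

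Finally, a stratified 3-df test is still an omnibus test and does not separate the fluid and oxytocin questions of section 1.0. That is true but a different issue. If the primary analysis were recast as a model with fluid and oxytocin terms, parity could be carried in it in the same way.

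None of this gives a reason to omit the factor, since the cost of including it is about 0.1 point of power at worst.

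**Conclusion.** The concern holds as a low-cost improvement, not a validity error. Parity is the only stated randomisation factor and the primary analysis does not use it. If parity is not prognostic, the current plan loses nothing. At a parity OR of 2 to 3 the planned test runs at about 4.2-4.7% instead of 5% and gives up roughly 0.3 to 1.5 points of power. At an OR of 6, the extreme examined, the level falls to 3.1-4.1% and the loss is 1.7 to 4.2 points.

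The direction follows from the design. The size rests on assumed parity ORs, an assumed parity mix, two parity strata, and reading the blocking as carried out within parity, which is its natural meaning.

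**What to change.** In section 4.0 .2:

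- Name one primary test: a 3-df Cochran-Mantel-Haenszel general-association test of endpoint by group, stratified by parity as used to randomise. Nulliparous/multiparous is the natural split from the eligibility text; section 3.0 .2.3 should confirm it.
- Obtain the Monte-Carlo exact p-value (10,000 samples) by permuting group within parity.
- Keep the unstratified cross-tabulation as the descriptive table.
- Optionally, add a supportive logistic regression with parity as a covariate and a 3-df group test, noting that its odds ratios are conditional on parity.

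The cost is one or two sentences. No further data or patients are needed, and the sample size need not change. If parity proves unrelated to the outcome, about 0.1 point of power is lost. Fixing the choice before unblinding also avoids a later choice between adjusted and unadjusted results.
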